Short Title	Adjuvant Radiation Therapy Omitting Primary Tumor Bed in Resected HPV-positive SCCA of the Oropharynx
Protocol Number	
Phase	Single-arm phase II
Study Duration	1 year
Study Center(s)	Single-center
Objectives	
Primary: To determine 2-year local (primary tumor site) control and toxicity rates in patients receiving adjuvant RT post-TORS, omitting the primary tumor bed, in patients with completely resected, HPV-positive SCCA of the oropharynx.
 
To determine acute and long-term toxicity rates in patients receiving adjuvant RT post-TORS, omitting the primary tumor bed, in patients with completely resected, HPV-positive SCCA of the oropharynx.
 
Secondary: To determine 2-year regional control, progression-free survival, metastasis-free survival, and overall survival.
 
To determine differences in QOL between patients treated with intensity-modulated photon radiation therapy versus proton beam radiation therapy

Number of Subjects	60
Diagnosis and Main Inclusion Criteria	T1-2 N1-2 M0, stage III or IVa SCCA of the oropharynx, negative for PNI, negative surgical margins

Study Regimen	EBRT (via IMRT or PBRT) will be delivered to at-risk regional lymph nodes, per standard of care. This study will omit EBRT treatment of the primary tumor bed.
Statistical Methodology	This is a single-arm phase II study assessing the safety (evaluated as local control and toxicity) of omitting adjuvant RT to the primary tumor site for selected patients with HPV-positive SCCA of the oropharynx. The analysis will be stratified by type of RT — IMRT (photon) and PBRT (proton), with the patients distributed between strata in a 1:1 ratio. We will estimate the distributions of time to local recurrence and time to toxicity by the Kaplan-Meier curve, and two-year locoregional control proportion and proportions experiencing toxicities by 95% exact confidence intervals. We will compare mean values of health-related quality of life (HRQoL) measures between strata using linear statistical models.

1 Introduction

This is a single-arm, phase II study examining the safety of omitting postoperative RT to the primary tumor bed in completely resected patients with locally-advanced, HPV+ oropharynx cancer.

The primary objectives of the study will be to determine 2-year local (primary site) control at the primary tumor site, and to determine 2-year RT-associated toxicity (as measured by CTCAE, version 4.0 and patient-reported QOL).

Secondary objectives of this study include determining 2-year regional control, progression-free survival, metastasis-free survival, and overall survival. Differences between intensity-modulated radiation therapy and proton therapy with respect to disease-related outcome and toxicity/QOL will also serve as secondary objectives.

Background, Preliminary Data, and Significance

Standard options for advanced-stage, HPV+, oropharyngeal cancer include either definitive chemoradiation or surgery followed by adjuvant radiation (+/- chemotherapy). The approach using TORS for the primary tumor resection followed by staged SND and adjuvant RT to the primary tumor bed and bilateral neck nodes has been pioneered at the University of Pennsylvania (1, 2). Disease outcomes are generally favorable, with overall survival of 90% (3), and locoregional control of 95–100% with either organ preservation RT (4), or with the TORS-based approach (5, 6); however, treatment-related morbidity can be significant. Definitive chemoradiation can result in long-term feeding tube use in up to 20% of patients (7), while 1 out of 4 patients who receive post-op RT after TORS resection experience ulceration and tissue breakdown at the primary resection bed as a late consequential effect of severe, acute mucositis (8). Approaches to decrease toxicities are therefore warranted.

One potential approach may be to omit post-op RT to the primary resection bed. A study from our group of 30 patients with oropharynx cancer (T1-2 in 83%) treated with surgery alone (TORS + SND) who refused adjuvant RT revealed a local control of 97% with surgery alone (9), calling into question the need to radiate the primary tumor bed in such patients. We will therefore conduct a pilot study of TORS alone to the primary tumor and SND followed by adjuvant RT (+/- Chemotherapy) to the regional nodes. The decision to add concurrent chemotherapy to postoperative radiation will be based on current standards of care, which recommend the addition of chemotherapy for the presence of either nodal extracapsular extension or positive margins (10). Margin positivity is an exclusion criterion for this study; therefore, the only indication for concurrent chemotherapy for this phase II study would be for nodal extracapsular extension.

This study is the first of its kind exploring such an approach in this patient population, and if high rates of locoregional control are obtained with less toxicity, it would potentially represent a paradigm shift in how patients with locally-advanced oropharynx cancer are managed.

This study will allow for RT to be given with either IMRT or PBRT (decision to treat with IMRT vs. PBRT not based on clinical features, but rather, insurance approval). Our initial patient experience with pencil-beam proton therapy reveals significant decreases in doses to critical organs at risk with no differences in coverage of radiation dose to at-risk tumor sites. For example, doses delivered to the oral cavity have consistently been reduced 10-fold with proton therapy compared to IMRT, with the first 2 patients reporting no changes in taste sensation near the end of their proton course.

We expect robust accrual to this protocol, as the Department of Otolaryngology performs over 800 resections annually for head and neck cancer, and the Department of Radiation Oncology treats over 200 patients annually with head and neck cancer. The majority of the patients receiving radiation do so after TORS and SND. We expect that approximately 150 patients annually will be eligible to participate on this study. Of these patients, based on current experience, approximately half will end up receiving IMRT, and half receiving PBRT, based solely on patient insurance carrier approval/denial of request for proton therapy (patient are not randomized to IMRT vs. PBRT).

We will prospectively administer patient-reported questionnaires to evaluate toxicity and quality of life to all patients, representing the first direct comparison of photon versus proton therapy for patients receiving head and neck radiation, and may potentially help define the standard RT modality for such patients.

2 Study Objectives

2.1 Primary Objective

- 2.1.1 Determine 2-year local control with omission of primary tumor bed RT.
- 2.1.2 Determine 2-year toxicity, as measured per CTCAE, version 4.0 and patient-reported HRQoL.

2.2 Secondary Objectives

- 2.2.1 Determine 2-year regional control, progression-free survival, metastasis-free survival, and overall survival
- 2.2.2 Determine differences between IMRT and proton therapy with respect to disease-related outcomes and toxicity/QOL

3 Study Design

3.1 General Design

This is a single-arm phase II study of post-op RT in the setting of locally-advanced HPV(+) oropharynx cancer. Only patients with small volume primary site disease (T1 or T2), resected with negative margins (2 mm or greater), without PNI, will be eligible.

- Patients will undergo post-op RT (+/- chemotherapy) to 60-66 Gy, per established clinical guidelines (10-12)
- P16 positivity via immunohistochemistry will be used as a surrogate for HPV positivity (standard of care practice at Penn)
- Regional nodes will be included in the RT field, as per current practice standards
- The primary tumor bed will be excluded from the RT field
- Platinum-based chemotherapy will be required for patients with evidence of extracapsular extension, based on current clinical guidelines (10-12)

3.2 Primary Study Endpoints

- 2 year local control
- 2 year toxicity

3.3 Secondary Study Endpoints

- 2 year regional control
- 2 year progression-free survival
- 2 year metastasis-free survival
- 2 year overall survival
- Differences in toxicity/QOL between IMRT and PBRT

4 Subject Selection and Withdrawal

4.1 Inclusion Criteria

- 4.1.1 Patients \geq 18 years old.
- 4.1.2 Histologically confirmed diagnosis of squamous cell carcinoma of the oropharynx, stage III or IVa, p16-positive on immunohistochemistry (determination of HPV status using p16 as surrogate is standard of care)
- 4.1.3 Pathologic T1 or T2 disease, resected with negative margins (\geq 2mm)
- 4.1.4 Pathologic N1, N2a, N2b, or N2c disease
- 4.1.5 ECOG Performance Status 0-1

- 4.1.6 Patients must sign an informed consent document that indicates they are aware of the investigational nature of the treatment in this protocol as well as the potential risks and benefits.
- 4.1.7 Ability to understand and the willingness to provide written informed consent.

4.2 Exclusion Criteria

- 4.2.1 Prior radiation therapy to the head and neck
- 4.2.2 Prior chemotherapy within the past 5 years
- 4.2.3 Presence of T3 or T4 disease
- 4.2.4 Presence of close (<2 mm) or positive margins
- 4.2.5 PNI on TORS resection of the primary cancer
- 4.2.6 LVI on TORS resection of the primary cancer
- 4.2.7 Presence of N0 disease in neck dissection
- 4.2.8 Presence of distant metastatic (M1) disease

- 4.2.7 Uncontrolled intercurrent illness including, but not limited to, symptomatic congestive heart failure, unstable angina pectoris, connective tissue disease or psychiatric illness/social situations that would limit compliance with study requirements.

4.3 Inclusion of Women and Minorities

The University of Pennsylvania Medical Center serves the metropolitan Philadelphia area, the surrounding suburban counties, southern New Jersey, and northern Delaware.

Inclusion of minorities: The University of Pennsylvania Cancer Center reports that minorities accounted for 14% of all patients (adult and pediatric) enrolled on therapeutic clinical trials. Furthermore, it is estimated that approximately 30% of cancer patients admitted to the Hospital of the University of Pennsylvania are minorities (source: University of Pennsylvania Cancer Center Grant). Female and male patients of all ethnic groups will be eligible for treatment in these protocols. Protocol accrual will be reviewed annually to include a determination of minority representation. An attempt will be made to enroll patients with larynx cancer in a distribution that matches the frequency of incident larynx cancer in the general population. The minority accrual estimates for our trial are based upon the total number of patients, the incidence rates of head and neck cancer, and estimates in the literature regarding minority accrual in clinical trials. A study by Tejada and Brawley (13) found that the accrual of American cancer patients to NCI-sponsored

treatment trials paralleled the incident disease burden among minorities. A report by Sikora et al. (14) indicates the distribution of incident head and neck squamous cell carcinoma to be 81.8%, 21.1%, 11.9%, 5.2%, 3.7%, 0.3%, and 0.8% among whites, all minorities, blacks, Asians, Hispanics, others and unknowns, respectively. The Philadelphia metropolitan area does not have a large American Indian or Alaskan population; therefore, no patients are estimated for this group.

Inclusion of women: Recruitment of patients will be through the University of Pennsylvania Cancer Center, Department of Radiation Oncology. All patients meeting study requirements will be approached for participation without discrimination. According to Cancer Facts and Figures (2011) from the American Cancer Society (15), new cases of larynx cancer were divided approximately 4:1 among male and female patients. Based on these and the above minority data, we estimate the accrual distributions for this trial shown below:

Ethnic Category	Males	Females	Total
Hispanic or Latino	2	1	3
Not Hispanic or Latino	46	11	57
Ethnic Category Total of All Subjects	48	12	60
Racial Categories			
American Indian/Alaska Native	0	0	0
Asian	2	0	2
Native Hawaiian or other Pacific Islander	0	0	0
Black or African American	12	2	14
White	34	10	44
Racial Categories: Total of All Subjects	48	12	60

Proposed Outreach Programs

The University of Pennsylvania Cancer Center has developed a number of minority outreach strategies. These include development of relationships with local community organizations, presentations or distribution of materials to local groups regarding trials, advertisements in minority newspapers and magazines, and presentations to professional organizations. If under-accrual of minority subjects is determined to be a problem, we will employ these methods to improve accrual. We will also make an effort to educate radiotherapists, surgeons, and medical oncologists who are working within our network and who serve minority populations about this trial.

4.4 Subject Recruitment and Screening

Patients will be recruited for possible participation in this study when they have been referred to the Department of Radiation Oncology at Penn for post-TORS adjuvant radiation therapy (+/- chemotherapy). The radiation oncologist will discuss participation in this study. The patient will be given an opportunity to read the consent form, ask questions and have them answered to their

satisfaction by the investigator or sub-investigator. At that time, if the patient indicates willingness to participate, the consent is signed by the patient and the investigator or sub-investigator obtaining consent. An eligibility checklist will be completed by the CRC to verify patient eligibility based on the criteria outlined in Section 4.1 and Section 4.2 and a subject ID number will be issued.

4.5 Clinical Evaluation and Staging Criteria

- History and Physical Examination
- Laboratory studies: pregnancy tests for women of child bearing age or potential prior to simulation for radiation therapy. (an urine pregnancy test prior to any radiation exposure is standard of care in the Department of radiation Oncology) .
- Staging studies are to include a chest x-ray, chest CT, or FDG PET/CT scan to evaluate for systemic metastases, performed 3 months prior to study entry. (standard of care)

4.6 Off-Study Criteria

- Extraordinary Medical Circumstances. If at any time the constraints of this protocol are detrimental to the subject's health, the subject will be removed from protocol therapy. In this event, the reasons for withdrawal will be documented.
- Subject's refusal to continue treatment. In this event, the reasons for withdrawal will be documented.
- Patients may be taken off study at any time at the discretion of the Principal Investigator
- Every effort will be made to follow subjects off study for toxicity and disease-related outcome

4.7 Study Duration

With an estimated accrual of 67 subjects per year, it is anticipated that accrual will continue for approximately 1.0 years. We believe this to be a conservative estimate, given the following:

5 Study Procedures

The Department of Otolaryngology performs over 800 resections annually for head and neck cancer, and the Department of Radiation Oncology treats over 200 patients annually with head and neck cancer. The majority of the patients receiving radiation do so after TORS and SND. We expect that approximately 150 patients annually will be eligible to participate on this study.

5.1 General study design

Sixty subjects will be enrolled on this single-arm Phase II study investigating the efficacy and safety of omitting postoperative RT to the primary tumor site in patients with locally-advanced (stage III or IVa) HPV+ oropharynx cancer who undergo TORS resection and neck dissection. Patients will be required to have a negative surgical margin (defined as 2mm or greater) after

resection of the primary site for a pathologic T1 or T2 cancer, with no evidence of perineural invasion.

Patients will be treated to the regional nodes, per current clinical standards, to a total dose of 60-66 Gy over 30-33 fractions, as determined by current clinical guidelines for postoperative radiation therapy (10-12). Both IMRT and PBRT will be allowed. Platinum-based chemotherapy will be delivered concurrently with RT, as clinically indicated for ECE (10-12).

Clinical, toxicity and QOL evaluations will be obtained at baseline (prior to RT), and completion of RT, and then at approximately 3, 6, 12, 18 and 24 months after completion of RT, during routine clinical follow-up appointments. Routine clinical follow-up will continue after this time point, at the discretion of the treating physicians.

Local recurrence will be defined as biopsy-proven recurrent squamous cell carcinoma at the original, primary tumor site.

Study Visit Schedule & Procedures

	*Baseline	End RT	**3mo. post RT	**6mo. post RT	**12mo. post RT	**18mo. post RT	**24mo. post RT
ICF	x						
Eligibility	x						
PE	x	x	x	x	x	x	x
QOL form	x	x	x	x	x	x	x
Tox. Assessment		x	x	x	x	x	x

*prior to RT ** approximately

5.2 Chemotherapy Administration

See above in section 5.1. Standard indications for the use of chemotherapy will be applied, as no part of this study will be examining any “off-label” uses of chemotherapy (including cetuximab, which is off-label in the adjuvant setting).

5.3 Radiation Therapy

Simulation for treatment is required. CT-based treatment planning is required. Treatment with either IMRT or PBRT is allowed. All fields will be treated every session. Interruptions in therapy should be discussed with the principal investigator but will be instituted at the discretion of the attending radiation oncologist.

Dose calculation should be performed using inhomogeneity corrections to account for differences in tissue density across the head and neck region. The total dose to regional lymph nodes will be 60-66 Gy to high-risk regions over 30-33 fractions, and 54 Gy to low-risk regions over 30 fractions. The primary tumor bed will be excluded from receiving high-dose radiation. Treatment will be continuous, 5 days per week for 6-7 consecutive weeks.

5.4 Study Visit Schedule

Please see above in section 5.1. Patients will be followed on study for a period of approximately 2 years after completion of RT, after which time, routine follow-up will continue “off-study” per the discretion of the treating physicians. Patients will be followed for short and long term RT-associated toxicity and local and /or regional recurrence.

6 Statistical Plan

Study design

A total of 60 patients will be accrued over a total of 1.0 year. Patients will be followed on study for a period of approximately 2 years after completion of RT. After this time, patients will continue to be seen in follow-up by their treating physicians, per physician discretion according to physician and institutional practices.

Patients will be enrolled into two non-randomized treatment strata: IMRT (photon) and PBRT (proton). We anticipate enrolling approximately 30 subjects in each stratum given our recent experience with patterns of insurance approval for PBRT versus IMRT (please see rationale described above in the introduction regarding IMRT vs. PBRT. Patients will not be randomized to IMRT vs. PBRT, but rather the decision to treat with one modality versus another is based on insurance carrier approval status. .

Data analysis plan

The primary objectives of the study are to estimate the 2-year local (primary site) control rate at the primary tumor site, and 2-year rates of RT-associated toxicities (as measured by CTCAE, version 4.0 and patient-reported QOL). We will estimate the distributions of time of loss of local control and time to RT-associated toxicity by exact 95% confidence intervals. We will compare the distributions of time to local recurrence and time to toxicity between strata by the logrank test.

Secondary objectives include determining 2-year regional control, progression-free survival (PFS), metastasis-free survival (MFS), and overall survival (OS). Differences between intensity-modulated radiation therapy and proton therapy with respect to disease-related outcomes and toxicity/HRQoL will also serve as secondary objectives. We will summarize data on regional control, PFS, MFS and OS using Kaplan-Meier curves; estimate proportions of toxicities by 95% exact confidence intervals; and make comparisons between treatment strata by the logrank test.

HRQoL evaluations will be obtained at baseline and completion of RT, and then approximately at 3, 6, 12, 18 and 24 months after completion of RT. We will estimate mixed linear models predicting HRQoL from treatment stratum, demographic and baseline clinical criteria. It is necessary to adjust for these factors to reduce potential confounding bias, as the treatments will not be randomized.

Sample size justification

With 30 patients per stratum, we will have 78% power to detect a difference in failure of 2-year local control, assuming a null rate of 5% and an alternative rate of 17.5%, using a one-tailed exact binomial test with type I error rate 10%.

Also with 30 patients per stratum, we will have 90% power to detect a difference in stratum means of HRQoL outcomes, provided that the effect size (absolute difference in means divided by common standard deviation) is larger than 0.86. This calculation assumes a two-tailed Student *t* test with type I error rate 5%.

Given that the decision to treat with IMRT vs PBRT is not randomized, but rather based on current insurance approval/denial patterns, we expect there to be an approximate 1:1 ratio of IMRT:PBRT; however, this study will not obligate 1:1 IMRT:PBRT. The comparison of IMRT to PBRT is a secondary objective of the study, and inability to populate the strata in a 1:1 ratio will not impede evaluation of the data for the primary objective. If recruitment goals are not met for each stratum, adjustments will be made to the data analysis as it pertains to the secondary objective of comparing IMRT to PBRT.

Interim analysis

We anticipate enrolling roughly 60 subjects over a period of 12 months, following each subject for up to 24 months. Because no patient will have reached the 24-month follow-up limit by the time enrollment ends, interim safety analyses will rely on model-based estimates of the rate of local recurrence using available time-to-event data. We will conduct an interim analysis for safety at the one-year mark (one year after completion of enrollment), when the median follow-up is 1.5 years (minimum = 1 and maximum = 2 years). We will fit an exponential model to the data on time to local recurrence. We will estimate the overall exponential hazard rate, comparing it to the null hazard rate of 0.00214 (predicting 5% recurrence at 24 months) in a two-tailed test with type I error rate 2.5% (to adjust for multiplicity). Should the estimated hazard rate significantly exceed the null rate, we will consider halting the trial for concern about safety. We will conduct the test when follow-up is complete (two years after completion of enrollment), again at the 2.5% type I error rate.

7 Safety and Adverse Events

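### Co-primary toxicity is limited to RT-associated events in some sections but not others, with no attribution rule, so primary-bed ulceration may be left out of the rate by judgement

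*Combined protocol and SAP*

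**What the plan says.** The co-primary toxicity endpoint appears in two forms.

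- **Limited to RT-associated events.** The introduction aims "to determine 2-year RT-associated toxicity (as measured by CTCAE, version 4.0 and patient-reported QOL". Section 5.4 states "Patients will be followed for short and long term RT-associated toxicity". The data analysis plan in Section 6 repeats the limit for the rate ("and 2-year rates of RT-associated toxicities (as measured by CTCAE, version 4.0 and patient-reported QOL") and for the time-to-event variable ("time to RT-associated toxicity by exact 95% confidence intervals").
- **Not limited.** Objective 2.1.2 reads "Determine 2-year toxicity, as measured per CTCAE, version 4.0 and patient-reported HRQoL". Endpoint 3.2 and the synopsis likewise refer to toxicity without regard to cause. Later sentences of Section 6, on the stratum comparison and the toxicity proportions, also drop the limit.

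No section defines RT-associated, names who attributes an event, or says how an ulcer in a resected bed is to be classed.

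Three other statements matter here. The background reports that one in four patients given post-operative RT after TORS "experience ulceration and tissue breakdown at the primary resection bed as a late consequential effect of severe, acute mucositis". Section 3.1 says "The primary tumor bed will be excluded from the RT field", whereas 5.3 excludes the bed only from high-dose radiation. Section 3.1 also says "Platinum-based chemotherapy will be required for patients with evidence of extracapsular extension".

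**The concern.** The trial leaves out bed RT partly to spare patients harm at the bed. Leaving it out also removes the most obvious reason for calling a bed ulcer RT-associated, and recent surgery at the same site is a ready alternative cause. Where platinum is given, it offers an alternative cause for mucositis. The limit therefore bears most heavily on the event the trial most needs to count.

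RT-attributed events are a subset of all events, so the filter can lower the trial's toxicity rate but cannot raise it. The direction favours omission. With a single arm, no concurrent group passes through the same filter. With both definitions in the document, the choice between them could also be made after the results are known.

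**Working it through.** **Plan's own figures.** None is given for the toxicity rate. The stated powers concern other endpoints and do not depend on this point. They reproduce closely: local control, rejecting at 4 or more failures in 30, gives an exact power of 79.5% (actual type I error 6.1%) against the stated 78%. HRQoL at effect size 0.86 gives 90.6% against the stated 90%.

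**Inputs for the illustration.** n = 60 (Section 6). The one-in-four rate, 25%, is from the background. The number of events called RT-associated is an assumption, because the documents give no share.

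**Formula.** Section 6 and the synopsis call for exact 95% intervals. For x events in n patients, the lower limit is the 2.5% quantile of Beta(x, n − x + 1), or 0 if x = 0. The upper limit is the 97.5% quantile of Beta(x + 1, n − x).

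**Case 1: omission brings no benefit.** 25% of 60 is 15 patients with bed ulceration.

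| Called RT-associated | Reported rate | Exact 95% CI | Excludes 25%? |
|---|---|---|---|
| 15 of 15 (same as all-cause) | 25.0% | 14.7% to 37.9% | No |
| 11 of 15 | 18.3% | 9.5% to 30.4% | No |
| 9 of 15 | 15.0% | 7.1% to 26.6% | No |
| 8 of 15 | 13.3% | 5.9% to 24.6% | Yes |
| 4 of 15 | 6.7% | 1.8% to 16.2% | Yes |
| 0 of 15 | 0% | 0% to 6.0% | Yes |

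Half of 15 is 7.5, taken as 8. The interval excludes 25% once 8 or fewer of the 15 are called RT-associated, that is, at 8/15 = 53% or below.

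**Case 2: omission does help.** Suppose 6 of 60 have bed ulceration: 10.0% (3.8% to 20.5%). If half are called RT-associated, the reported rate is 3 of 60: 5.0% (1.0% to 13.9%). The direction of the conclusion is unchanged, but the estimate is halved.

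**The case against.** **The term is undefined, so nothing is excluded outright.** A reader might infer that bed ulcers drop out by definition. The documents do not support that. An assessor could still call an ulcer RT-associated, since the background itself traces such ulcers to mucositis after RT. A reader might also infer that the bed receives no radiation. Section 3.1 points that way, but 5.3 excludes only high dose, so some dose is not ruled out. This part of the objection stands: loss would come through case-by-case judgement.

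**Events are still seen.** The adverse event definition in 7.1 does not depend on cause, grade 3 or higher events go to the DSMC process, the Medical Monitor sees all adverse events, and patient-reported QOL needs no attribution. These are real safeguards for patients, but they do not correct the reported co-primary rate.

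**No test against 25% is planned.** This is true; Section 6 estimates toxicity rates only. But the background says that high control with less toxicity could change practice, which implies at least an informal comparison with past rates. How the cited study counted or attributed ulcers cannot be seen, so it cannot be claimed that the filter acts on one side only.

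**The IMRT versus PBRT comparison.** A reader might infer that investigators who know the modality will bias it. The documents do not say who attributes events, and the planned comparison of time to toxicity is worded without the limit. That inference is not supported.

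**An all-cause count takes in surgical healing.** This stands, and is why baseline findings must be separated.

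**Conclusion.** The point holds as an inconsistent co-primary definition with no attribution rule. It is more than a gap in wording, because Section 6 states a restrictive counting rule that can leave the motivating harm out of the rate, in the direction that favours omission. The possible size is large: a true 25% could be reported as anything from 25% down to 0%. If about half the events are attributed to RT, it becomes 13.3%, with an interval that excludes 25%. This rests on assumed shares and on omission bringing no benefit; the documents give neither an all-cause rate under omission nor an attribution share. It should be corrected before analysis. The stated power figures are unaffected.

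**What to change.** 1. Use one definition in Section 1, 2.1.2, 3.2, 5.4 and Section 6. Count CTCAE v4.0 events that are new or worse than baseline, from the start of RT to 24 months after RT, at the toxicity visits already scheduled and regardless of attributed cause.
2. Name ulceration or tissue breakdown at the primary bed as included.
3. Report the RT-attributed subset as a supportive table.
4. Align the visit table in 5.1, which shows no baseline toxicity assessment, with the text of 5.1 and with 8.3, which both provide for one. Surgical findings present before RT can then be separated.
5. State that the adverse event reporting period in 7.1, which ends 30 days after the last treatment, does not limit data collection for this endpoint.
6. Reconcile 3.1 and 5.3 on how the bed is excluded.

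The cost is mostly wording, with no added visits. An attribution field may be needed on the toxicity form. Rates will be somewhat higher because events related to surgery and chemotherapy are included.
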